#### **9.6 Death on Study**

Any death occurring between the study inclusion and 30 days following the last radiotherapy treatment must be reported as a SAE within 7 days, regardless of the relation to the radiotherapy. Death occurring during the study follow-up period (i.e. later than 30 days after the last infusion) need only to be reported as serious adverse event if it is thought that there is a possible relation to the radiotherapy (possible, probable). All deaths should be reported on the death report form section on the CRF regardless of cause.

#### **10.1 RECIST 1.1 criteria for response**

*Complete response (CR):* Disappearance of all clinical evidence of tumor (target and non-target lesions), determined by two observations not less than four weeks apart.

*Partial response (PR):* 30% or greater decrease in the sum of the longest diameter of target lesions, determined by two observations not less than 4 weeks apart. No unequivocal increase in the size of non-target lesions or the appearance of new lesions may occur.

*Stable disease (SD):* Steady state of response (i.e. not PR and not PD) of at least 9 weeks duration. There may be no appearance of new lesions for this category.

*Progressive disease (PD):* 20% or greater increase in the sum of the longest diameter of target lesions or unequivocal progression of non-target lesions. Appearance of new lesions will also constitute progressive disease.

The duration of response will be measured from the time measurement criteria are met for CR/PR until the first date the recurrent or progressive disease is objectively documented.

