#### **4.1.1 Primary Objective**

Toxicity (eg cardiac and pulmonary toxicity).

Local control at 5 years. Local control is defined as freedom of locally progressive disease; ie CR (complete remission) or SD (stable disease) based on CT or PET/CT evaluation

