#### **4.1.2 Secondary Objective**

Overall survival, progression-free survival, relapse pattern, quality of life measured with QLQ 30 + LC 14.

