## **6.2 Inclusion Criteria**

- Histological or cytological diagnosis of thymoma or thymic carcinoma
- With radical surgery stage III, IVa and selected stage II with type B2, B3 or thymic carcinoma according to local routine
- With non-radical surgery (R1 or R2), stage I - IVa, any histology
- Medically inoperable, or patient refusing surgery, stage I - IVa, any histology
- PS WHO 0 - 2.
- $FEV_1 \geq 1L$  or  $\geq 40\%$  of predicted and CO diffusion capacity  $> 40\%$  of predicted (post-operative measures).
- Age  $\geq 18$  years, no upper age limit.
- Written informed consent from patients.

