#### 7.5 Schedule of assessments

Table 1

	Prior to RT	During RT	End of RT	Within 2 weeks from RT	4 weeks
Medical history	X				
Physical examination	X	X	X		X
Weight & PS	X	X	X		X
NT-Pro-BNP, TNT, CRP	X	X	X		X
Hematology	X		X		X
Creatinine, calcium, albumin, bilirubin, ALP, ASAT, ALAT, LDH	X		X		X
Electrocardiogram	X	X	X	X	X
PET-CT-scan	optional				
Tumor assessment by CT 	X				
TTE/UCG	X			X	

Spirometry 	X				
Assessment symptoms and toxicity	X	X	X		X
QLQ 	X		X		

	4 months from RT	6 months from RT	Follow up	End of study	
Medical history					
Physical examination	X		X	X	
Weight & PS	X		X	X	
NT-Pro-BNP, TNT, CRP	X		X	X	
Hematology	X		optional		
Creatinine, calcium, albumin, bilirubin, ALP, ASAT, ALAT, LDH	X		optional		
Electrocardiogram	X		X	X	
PET-CT-scan	optional				
Tumor assessment by CT 	X		X	X	
TTE/UCG	X			X	
Spirometry 		X		X	
Assessment symptoms and toxicity	X		X	X	
QLQ 	X	X	X	X	

1. CT scan will be performed before inclusion (not older than 4 weeks), at 4, 7, 10 and 13 months after therapy and every 6 months thereafter during follow up or until progressive disease.
2. Quality of life will be measured by using QLQ C30 and LC14 module at baseline, week 3 of treatment, end of treatment ,1, 3, 6 and 12 months after completion of therapy. Thereafter at 2, 3 and 5 years after treatment.
3. Spirometry including CO diffusion capacity will be performed before inclusion, after 6 months and at end of study

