### 8.2 Planning Target Volume

The different volumes of interest shall be defined in agreement with ICRU 78.

OAR's: heart, LADCA ,lung, spinal cord, esophagus

Gross Tumour Volume (**GTV**):

Visible tumour growth

Clinical Target Volume (**CTV**):

Post-operative tumour bed and/or defined margin to GTV: 0,5 cm to lung tissue and 1 cm elsewhere. Adjustment to airways, big vessels, bone will be performed. No adjuvant volumes, except for pleura/pericardium in between separate GTV's (stage IVa)

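### The primary endpoint of 5-year local control has two conflicting readings: a local definition, and a CR-or-SD test whose only definitions in the protocol apply to the whole patient

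*Protocol*

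**What the plan says.** Protocol section 4.1.1 makes 5-year local control a primary objective alongside toxicity, and defines it in one sentence: "Local control is defined as freedom of locally progressive disease; ie CR (complete remission) or SD (stable disease) based on CT or PET/CT evaluation".

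Response categories are defined in one place only, section 10.1, which the table of contents puts under the criteria for efficacy:

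- Complete response: "Disappearance of all clinical evidence of tumor (target and non-target lesions), determined by two observations not less than four weeks apart".
- Stable disease, on new lesions: "There may be no appearance of new lesions for this category".
- Progressive disease, on new lesions: "Appearance of new lesions will also constitute progressive disease".

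None of these is limited to the treated site, and section 10.1 gives no local or in-field version.

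Relapse at any site is covered by other endpoints. Section 4.1.2 lists the secondary objectives: "Overall survival, progression-free survival, relapse pattern, quality of life measured with QLQ 30 + LC 14".

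Section 6.2 admits advanced local disease, for example "With non-radical surgery (R1 or R2), stage I - IVa, any histology". The target in section 8.2 is restricted: "No adjuvant volumes, except for pleura/pericardium in between separate GTV's (stage IVa".

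On imaging, section 7.5, Table 1, footnote 1 has CT "every 6 months thereafter during follow up or until progressive disease". Sections 5.6 and 7.3 also schedule six-monthly CT but state no stop at progression.

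**The concern.** Section 4.1.1 opens with a local idea and closes with an operational test, and the two can disagree for the same patient. A new pleural or distant deposit outside the treated volume, with a clear tumour bed, is not local progression. Yet under section 10.1 that patient has progressive disease and can be neither CR nor SD.

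Such a patient is foreseeable. Stage IVa (pleural or pericardial metastases, Appendix 14.4) and thymic carcinoma are eligible, section 3.0 describes thymic carcinoma as more prone to distant spread, and most of the pleura is left untreated by design.

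Two things are at stake. The primary efficacy estimate would depend on which half of the sentence a reader applies. And if CT really ends at any progression, local status after a non-local relapse may never be observed, which no later analysis could repair.

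**Working it through.** **1. The plan's own figure.** The only number attached to this endpoint is 40 patients (section 11.0). It comes with no reference rate, margin, error rate or power, so there is nothing to reproduce, and nothing here contradicts it. The check is mainly one of wording.

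**2. The two readings applied to typical patients.**

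| Patient at follow-up | Local phrase in 4.1.1 | CR-or-SD test by 10.1 |
|---|---|---|
| No lesion at any site | Controlled | Passes |
| Recurrence inside the treated volume | Failure | Fails (PD) |
| Treated site clear, new lesion outside the volume only | Controlled | Fails (PD) |

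The readings part only in the third row.

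**3. Resected patients.** After radical surgery there is normally no target lesion. There is then no sum of diameters to follow, and a local recurrence would itself appear as a new lesion. The new-lesion rule therefore decides the outcome, and section 10.1 does not ask whether the lesion lies in the treated volume. For the same reason, deleting the rule would be wrong. What is missing is the site.

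**4. Effect per patient.** With n = 40, one reclassified patient changes a simple proportion by 1/40 = 2.5 percentage points.

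**5. Illustration.** Let L be the number of local failures and D the number of patients with only an out-of-field relapse. The local reading gives (40 − L)/40 and the CR-or-SD reading gives (40 − L − D)/40, so the gap is D/40. The values of L and D below are assumptions, because the protocol supplies neither. Intervals are Clopper-Pearson 95%.

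| L | D | Local reading | CR-or-SD reading | Gap |
|---|---|---|---|---|
| 4 | 2 | 36/40 = 90% (76.3–97.2) | 34/40 = 85% (70.2–94.3) | 5 points |
| 4 | 4 | 90% | 32/40 = 80% (64.4–90.9) | 10 points |
| 4 | 8 | 90% | 28/40 = 70% (53.5–83.4) | 20 points |
| 2 | 2 | 38/40 = 95% (83.1–99.4) | 36/40 = 90% (76.3–97.2) | 5 points |
| 2 | 4 | 95% | 34/40 = 85% (70.2–94.3) | 10 points |
| 2 | 8 | 95% | 30/40 = 75% (58.8–87.3) | 20 points |

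The gap depends on D alone, not on the assumed local failure rate. These are plain proportions. The planned Kaplan-Meier analysis would also involve censoring, so they show scale and do not predict the result.

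**6. Imaging.** Footnote 1 of Table 1 names progressive disease without limiting it to local progression. Read with section 10.1, an out-of-field lesion could end CT. Read with sections 5.6 and 7.3, CT would continue. Only the second course lets 5-year local status be seen in the patients on whom the readings disagree.

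**The case against.** The strongest reply is that the opening phrase of section 4.1.1 governs and the CR-or-SD clause is loose shorthand for no local progression. There is good support for this:

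- The clause omits partial response. Section 10.1 defines SD as neither PR nor PD, so a literal reading would fail a patient whose treated tumour shrank by 30% or more, which cannot be intended.
- Sections 4.1.1 and 10.1 do not cite each other. One speaks of complete remission on CT or PET/CT; the other speaks of complete response and does not mention PET.
- The new-lesion sentence is not an error in itself, since PFS needs a rule of that kind.
- Relapse pattern is already a secondary objective, so relapse site should be collected and local failure might be separated at analysis.

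Much of this stands. The link to section 10.1 is inferred, and a reader might go too far and conclude that the protocol simply counts every out-of-field relapse as a local failure. The opening phrase of section 4.1.1 does not allow that.

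Two further inferences are also unsupported. One is that local control merely repeats PFS: section 4.1.2 does not define PFS. The other is that comparison with historic data becomes impossible: section 11.0 does not say which endpoint will be compared, and the definitions used in those sources are not at hand.

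What does not stand is that the ambiguity is harmless. Anyone told to score CR or SD has no definition but section 10.1. The omission of PR is another reason to replace the clause. And separating local failure at analysis works only if local imaging continues after non-local progression, which footnote 1 leaves in doubt.

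**Conclusion.** The point holds as a conflict inside the definition of the primary endpoint, located in section 4.1.1 read with section 10.1. A patient with only an out-of-field relapse is controlled by the local phrase and a failure by the stated CR-or-SD test, and the protocol does not settle which applies. It does not hold as a flat statement that such patients fail.

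The size is 2.5 points per affected patient at n = 40. Any total, such as 5 to 20 points for 2 to 8 patients, rests on assumed counts and ignores censoring and death.

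This is more than detail left for an analysis plan. The protocol itself states a test that, if followed, would misclassify patients on a primary endpoint, and its CT footnote could leave the correct status unobserved. It should be fixed in the protocol.

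**What to change.** 1. In section 4.1.1, replace the CR-or-SD clause with a definition by site. Local failure is progression of a treated lesion, or a new lesion within or at the margin of a stated treated volume. Name that volume: the PTV, or the CTV/ITV where robust optimisation is used, since the note to Table 2 allows PTV objectives to be set aside in that case. For resected patients without measurable disease, local control is the absence of such a lesion.
2. State that lesions wholly outside that volume count for PFS and relapse pattern only.
3. State how non-local relapse and death enter the local-control estimate, for example as competing events.
4. Keep the section 10.1 categories, including the new-lesion rule, for overall response and PFS.
5. Reconcile footnote 1 of Table 1 with sections 5.6 and 7.3, so that local status is still observed after non-local progression.

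The cost is small: amendment wording, one CRF item recording relapse as inside, at the margin of, or outside the treated volume, and some continued reading of scheduled CTs after non-local progression. The target volumes are already recorded (section 8.2), CT is already scheduled, and relapse pattern is already an objective.

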## **10.2 Safety analysis**

A safety analysis regarding toxicity will be performed by the principal investigator after inclusion of 15 subjects. The analysis will be focused on the frequency of unwanted side effects and their severity.

## **10.3 Quality of life analysis**

Quality of life will be measured by using QLQ C30 and LC14 module at baseline, week 3 of treatment, end of treatment ,1, 3, 6 and 12 months after completion of therapy. Thereafter at 2, 3 and 5 years after treatment.

## **11.0 Statistics**

We will perform a Kaplan-Meier analysis with the aim to compare our data with published historic data from the ITMIG international database and other datasets. Since there is a limited amount of published thymoma data concerning heart we will also try to relate heart toxicity with published data from Hodgkin and breast cancer studies. Toxicity data will be analysed descriptively and there will be a comparison between the proton patients and photon control group. 40 patients will be included in the study

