### **3.0 Introduction and background**

Thymic epithelial tumours (TETs or thymic malignancies) which comprise thymoma and thymic carcinoma, are rare cancers worldwide. The annual incidence is approximately 0.15/100.000 in the United States (1) and 0.32/100.000 in the Netherlands (2). According to the Swedish National Cancer Register 33 patients were diagnosed with either thymoma or thymic carcinoma in 2013 which is an approximative incidence of 0.33/100.000. TETs are heterogenous both morphologically as well as clinically. Thymomas may be associated with a spectrum of autoimmune conditions, whereas this is rare in thymic carcinomas. Thymic carcinomas are more prone to distant metastatic spread. In a Japanese retrospective analysis the survival rates differs between the groups with a median OS of patients with thymoma of 235 months compared with 32 months for those with thymic carcinomas (3) which is comparable with other reports. There is no official stage classification for thymic malignancies defined by the Union Internationale Contre le Cancer (UICC) and the American Joint Commission for Cancer (AJCC). ITMIG in collaboration with the International Association for the Study of Lung Cancer (IASLC) have published a proposal for a new staging system for the forthcoming edition of the TNM classification of Malignant Tumors (4-5). Until this system is

definitely defined ITMIG has proposed staging according to the Masaoka-Koga stage classification (6) which is generally spread and used worldwide.

Surgery remains the cornerstone in the management of TETs. Minimally invasive techniques including thoracoscopic and robotic surgery for early stage disease are gradually increasing. Chemotherapy, although often with a moderate response, has a role in downstaging as well as managing more advanced disease. There is also evolving data on targeted drugs. The role for radiotherapy is a matter of ongoing debate but the use of postoperative radiotherapy (PORT) after incomplete surgery and/or advanced stage (III/IV according to Masaoka) is more or less standard (7-9). There is considerably less evidence and weaker consensus for the efficacy of PORT of stage II patients (10) and the use of it varies worldwide. It could, however, be used in selected cases such as B3 and C patients in accordance with local routines.

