## **5.0 Study Design**

### **5.1 Description**

This is an open, non-randomized multicentre, phase II trial, to investigate the efficacy and toxicity in PBS proton therapy of thymic malignancies

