### **5.3 Treatment Schedule**

The study population will consist of three patient categories;

**A** patients who have undergone radical surgery

**B** patients who have undergone non-radical surgery

**C** patients who are considered inoperable.

Radiotherapy doses will differ between the groups. We have assumed that RBE for protons is 1.1 and the prescribed dose is the corresponding dose for photons (Gy(RBE)). Within brackets is the physical dose.

Patients who have undergone radical surgery but has an unfavorable histology (B2, B3, C) and/or Masaoka stage III or IVa (selected stage II-patients can be considered according to local practice) will receive 2 Gy(RBE) once daily, five days a week to a total dose of 50 Gy(RBE) (1.82 Gy OD, total dose 45.5 Gy)

Patients who have undergone non radical surgery (R1), regardless of stage and histology, will receive 2.3 Gy(RBE) once daily, five days a week, to a total dose of 57.5 Gy(RBE) (2.09 Gy OD, total dose 52.25 Gy)

Patients who are considered medically inoperable, or refuses surgery, regardless of stage and histology, and patients who have undergone R2 non-radical resection will receive 2.5 Gy(RBE) once daily, five days a week, to a total dose of 62.5 Gy(RBE) (2.27 Gy OD, total dose 56.75 Gy)

Patients not willing to participate in study, but willing to be included in follow-up according to study protocol will receive photon therapy according to local practice. The total dose must be  $\geq 45$  Gy.

Up to three cycles of chemotherapy may be administered prior to start of radiation according to local practice. Radiation therapy shall then start within 4-6 weeks after completion of the third cycle. Use of concomitant chemotherapy is not allowed.

If surgery has been performed, radiation therapy shall start 4-8 weeks thereafter

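### The historic comparison in section 11 is not tied to the trial's mix of histology and resection category, so a proton effect cannot be separated from case mix

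*Protocol*

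**What the plan says.** Section 11.0 of the protocol, repeated under statistical methods in the synopsis, states one efficacy analysis: Kaplan-Meier, with the aim to "compare our data with published historic data from the ITMIG international database and other datasets". It adds that "40 patients will be included in the study". The photon group appears only in the sentence on toxicity.

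The design is set out in section 5.1: "This is an open, non-randomized multicentre, phase II trial, to investigate the efficacy and toxicity in PBS proton therapy of thymic malignancies". Local control at 5 years is a primary endpoint (section 4.1.1). Overall and progression-free survival are secondary (section 4.1.2).

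The cohort is mixed in three respects:

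- **Histology.** Entry requires "Histological or cytological diagnosis of thymoma or thymic carcinoma" (section 6.2), with no quota for either. Section 3.0 quotes a "median OS of patients with thymoma of 235 months compared with 32 months for those with thymic carcinomas".
- **Resection and dose.** "The study population will consist of three patient categories" and "Radiotherapy doses will differ between the groups" (section 5.3). The prescribed total is 50 Gy(RBE) after radical surgery, 57.5 after R1 resection, and 62.5 after R2 resection or in inoperable patients. No planned numbers per group are given.
- **Stage.** One criterion reads "With non-radical surgery (R1 or R2), stage I - IVa, any histology". Stage II after radical surgery enters according to each centre's routine (section 6.2).

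**The concern.** In a single-arm trial compared with published series, the series is the control, so the choice of series and its likeness to the trial cohort are part of the design. Here the reference is open-ended, and nothing in section 11.0 links it to the histology, resection status or stage of the patients who will enrol. Those features carry prognosis, and resection status also determines the dose. If the reference series has a different mix, the pooled curve will differ from it even when protons and the historic treatment perform identically. A real difference could equally be hidden.

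This bears on the stated objective in section 4.1, which is to explore whether proton therapy is feasible and gives acceptable local control. Section 11.0 offers no other comparison by which to judge whether the local control observed is acceptable.

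**Working it through.** The plan has no figure of its own to reproduce on this point: it gives no reference rate. The check therefore asks how far a difference in histology mix alone could move a pooled 5-year rate. It can be done only for overall survival, the one outcome for which the protocol gives figures by histology.

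**Inputs**

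- Median OS of 235 months (thymoma) and 32 months (thymic carcinoma): section 3.0.
- n = 40: section 11.0.
- Time point of 60 months, matching the 5-year horizon of section 4.1.1.
- Assumed: exponential survival, no censoring before 5 years, and carcinoma shares of 10% to 40%. The protocol states no share for the trial or for any historic series.

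**Step 1. 5-year OS by histology**, S(60) = 0.5^(60/median)

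- Thymoma: 0.5^(60/235) = 0.838
- Thymic carcinoma: 0.5^(60/32) = 0.273
- Difference: 0.565

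**Step 2. Pooled rate and its precision.** With carcinoma share f, S = (1 − f) × 0.838 + f × 0.273. The standard error is √(S(1 − S)/40) and the 95% half-width is 1.96 times that.

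| Carcinoma share | Patients of 40 | Pooled 5-year OS | Standard error | 95% half-width |
|---|---|---|---|---|
| 10% | 4 | 78.1% | 6.5 points | 12.8 points |
| 20% | 8 | 72.5% | 7.1 points | 13.8 points |
| 30% | 12 | 66.8% | 7.4 points | 14.6 points |
| 40% | 16 | 61.2% | 7.7 points | 15.1 points |

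**Step 3. Shift from mix alone**

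- 10-point difference in share (4 of 40 patients): 0.10 × 56.5 = about 5.7 points.
- 20-point difference (8 of 40), for example 10% against 30%: 78.1 − 66.8 = 11.3 points. This exceeds one standard error (about 7) and is slightly below the 95% half-width (about 13 to 15).

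The direction does not need the exponential form. At 60 months a group with median 235 months is still above 50% survival, and a group with median 32 months is already below it.

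**Step 4. Would reporting by subgroup alone be enough?** Three equal groups would hold about 40/3 = 13 patients each. At assumed 5-year rates of 70% and 90%, the half-widths are 1.96 × √(0.7 × 0.3/13) = 25 points and 1.96 × √(0.9 × 0.1/13) = 16 points. Two histologies by three resection groups would average 40/6 = 6.7 patients per cell. Subgroup results alone would therefore be imprecise. A whole-cohort comparison against a reference weighted to the trial's own mix keeps all 40 patients.

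**What cannot be computed.** The protocol gives no local-control rate by histology, stage or resection status. The shift for the primary endpoint, and any shift due to resection or dose group, cannot be sized.

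**The case against.** The strongest reply is that section 11.0 is only an outline. It does not say the comparison will be crude, and a statistical analysis plan, which may exist but is not at hand, could stratify or standardise. That is fair as to technique. It does not remove the point, because the protocol itself fixes an open-ended external reference as its only stated efficacy comparison for a deliberately mixed cohort.

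Other parts of the reply stand and limit the claim:

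- **Endpoint.** All the arithmetic concerns OS, which is secondary. Section 3.0 says carcinomas are more prone to distant spread, so an OS gap need not carry over to local control. A reader might infer that 5-year local control would shift by 11 points; the documents do not support that.
- **Source of the medians.** They come from one retrospective analysis, listed as single-institution, whose stage mix is not given. This trial excludes stage IVb.
- **Sampling error.** A reader might infer that the artefact exceeds sampling error. It exceeds one standard error, but not the 95% half-width, and the 20-point difference in mix is itself an assumption.
- **Historic mix.** A reader might infer that the ITMIG database is known to differ. Its mix is not in the documents, nor is whether its published results are already stratified.
- **Feasibility.** Standardising over every combination of histology and resection group may not be possible with the published rates available.

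The aim is also exploratory, with no success threshold, and a 5-year estimate has descriptive value in itself. False-positive rates for a claim of better or worse control would require a formal test that the protocol does not contain, so none is claimed here.

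**Conclusion.** The point holds in a limited form. As written, the historic comparison cannot separate a proton effect from differences in case mix. A reader might go further and infer that the result will reflect case mix instead of protons. The documents do not show that: a proton effect may exist, and the comparison simply cannot isolate it.

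For OS, a histology imbalance could plausibly be comparable to the trial's own statistical uncertainty. That rests on the two quoted medians, exponential survival and assumed carcinoma shares. For local control, and for the resection and dose groups, the argument applies in kind but its size is unknown.

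**What to change.** Amend section 11.0 as follows:

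1. Name the comparator dataset or datasets before the first local-control analysis.
2. Report local control, PFS and OS separately for thymoma and thymic carcinoma, and descriptively by resection category (R0, R1, and R2 or inoperable, the split by which section 5.3 assigns dose).
3. Compare the whole-cohort 5-year rate with an expected rate: the sum over strata of the trial's own share in the stratum times the published historic rate there. Use histology at least, and resection status as well where published rates exist.
4. Where no matching historic rate exists, label the comparison descriptive and draw no efficacy conclusion from it.

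The cost is a few sentences and a small extra analysis. Histology and resection status are already needed for eligibility and group assignment, so no new data are collected. The drawbacks are wide intervals in small strata and dependence on what stratum rates have been published.
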